12.5. Pharmacokinetic Analysis

Pharmacokinetic analyses in Part 1 will be based on the PK analysis set, and all analysis and reporting of plasma concentration and PK parameter data will be performed separately for each analyte. Blood samples for PK analysis will be collected as outlined in Table 9-1 to determine G1T38, and osimertinib plasma concentrations. Plasma concentration data will be tabulated descriptively and graphed at each visit and time point.

The pharmacokinetic parameters for G1T38 presented in Table 10-4 will be calculated with noncompartmental methods (WinNonlin Version 6.3 or higher) based on the plasma concentration-time data. Pharmacokinetic parameters will be summarized descriptively by visit and analyte.

The potential effects of steady-state administration of osimertinib on the single-dose PK profile of G1T38 will be assessed by ANOVA on the ln-transformed AUC_{inf} and C_{max}. The ANOVA will include treatment as a fixed effect, and subject as a random effect. Each ANOVA included calculation of least squares means (LSM), the difference between treatment LSM, and the standard error associated with this difference. The osimertinib DDI will be assessed using G1T38 plus osimertinib (Test) versus G1T38 alone (Reference). The 90% CIs for the ratios will be derived by exponentiation of the CIs obtained for the difference and the CIs will be expressed as a percentage of Test relative to the Reference.

13. QUALITY CONTROL AND QUALITY ASSURANCE

An eCRF must be completed for each patient enrolled. Once a patient is no longer on the study and the eCRF is completed, the principal investigator will be required to review and sign the eCRF for that patient. The investigator shall ensure the accuracy, completeness, legibility, and timeliness of the data reported to the sponsor in the eCRFs and in all required reports.

Accurate and reliable data collection will be assured by verification and cross-check of the eCRFs against the investigator's records by the study monitor (source document verification), and the maintenance of a drug-dispensing log.

14. ETHICS AND PROTECTION OF HUMAN PATIENTS

14.1. Ethical Conduct Statement

The investigator will ensure that this study is conducted in full conformance with the principles of the Declaration of Helsinki (as amended in Tokyo, Venice, Hong Kong, and South Africa) or with the laws and regulations of the country in which the research is conducted, whichever affords the greater protection to the individual. The investigator will ensure adherence to the basic principles of GCP as outlined in the current version of 21 Code of Federal Regulations (CFR), subchapter D, part 312, Responsibilities of Sponsors and Investigators, part 50, Protection of Human Subjects, and part 56, Institutional Review Boards, and ICH E6 GCP. The investigator will follow all national, state, and local laws of the pertinent regulatory authorities.

14.2. Independent Ethics Committee/Institutional Review Board

The protocol and all associated amendments and consent/assent materials will be reviewed and approved by the investigative site's local IEC/IRB or a central IEC/IRB. It is the investigator's responsibility to obtain approval of the study protocol and informed consent, and any other study related materials such as advertising or information leaflets, from their IEC/IRB prior to initiating the study. Approval must be obtained in writing via a letter identifying the protocol, the date of the IEC/IRB meeting, and the date of approval.

14.3. Informed Consent

It is the responsibility of the investigator to obtain written informed consent from each patient participating in this study, after adequate explanation of the goals, methods, potential benefits, and hazards of the study. The investigator or designee must also explain that the patients are allowed to withdraw from the study at any time and for any reason. All patients should be given a copy of the informed consent and any updates. Original signed consent forms will be maintained at the site and be made available for inspection, as appropriate.

14.4. Patient Confidentiality

The investigator must assure that patients' anonymity will be maintained and that their identities are protected from unauthorized parties. Patient names will not be supplied to the sponsor and only the patient number will be recorded in the eCRF and study findings stored on a computer will be stored in accordance with local data protection laws. The patients will be informed that representatives of the sponsor, IEC/IRB, or regulatory authorities may inspect their medical records to verify the information collected, and that all personal information made available for inspection will be handled in strictest confidence and in accordance with local data protection laws.

14.5. Adherence to the Protocol

The study shall be conducted as described in this protocol, except for an emergency situation in which proper care of the patient requires immediate alternative intervention. The protocol will be provided to the IEC/IRB and appropriate local regulatory authorities for approval.

Any protocol amendments will be done in accordance with the provisions agreed upon in Section 14.6. Any deviation from the design of the study as set forth in this document will be recorded as a protocol deviation and will be explained in detail as it occurs and/or is detected.

14.6. Protocol Amendments

All protocol amendments (both nonsubstantial and substantial amendments) must be submitted to the appropriate IEC/IRB and competent authorities (as required) in accordance with local requirements. Approval for substantial amendments must be received in writing before changes can be implemented (ie, if the risk benefit ratio is affected and/or the modification represents a change in basic study definitions such as objectives, design, sample size, and outcome measures, etc.), except for those changes which would decrease risk to the patient.

14.7. Patient Compliance

Patients must be available for all scheduled study visits. Any reason for patient noncompliance will be documented.

15. DATA HANDLING AND RECORD KEEPING

15.1. Data Collection and Retrieval

This study will use a 21 CFR Part 11 compliant electronic data capture system. An eCRF will be used for data recording. All data requested on the eCRF must be entered and all missing data must be accounted for.

Accurate and reliable data collection will be assured by verification and cross-check of the eCRF against the investigator's records by the study monitor (source document verification), and the maintenance of a study drug-dispensing log by the investigator.

Before study initiation, at a site initiation visit or at an investigator's meeting, a sponsor representative will review the protocol and eCRFs with the investigators and their staff. During the study, a monitor will visit the site regularly to check the completeness of patient records, the accuracy of entries on the eCRFs, the adherence to the protocol and to GCP, and the progress of enrollment. The monitor will ensure during on-site visits that study drug is being stored, dispensed, and accounted for according to specifications. Key study personnel must be available to assist the monitors during these visits.

The investigator must give the monitor access to relevant hospital or clinical records to confirm their consistency with the eCRF entries. No information in these records about the identity of the patients will leave the study center. Monitoring standards require full verification for the presence of informed consent, adherence to the inclusion/exclusion criteria, documentation of SAEs, and the recording of primary efficacy and safety variables.

15.2. Investigator Reporting Requirements

Local regulations may require the investigator to provide periodic safety updates on the conduct of the study and to notify the IEC/IRB of study closure. Such updates and notifications are the responsibility of the investigator.

15.3. Records Retention

After closure of the study, the investigator will maintain copies of all study records (ie, investigator files and patient files) in a secure location. The investigator's study file will contain the protocol, protocol amendments, eCRF and query forms, IEC/IRB and governmental approval with correspondence, informed consent, drug records, staff curriculum vitae and authorization forms, and other appropriate documents and correspondence.

Patient clinical source documents may include (but not limited to) patient hospital records, physician's and nurse's notes, original laboratory reports, ECG, electroencephalogram, X-ray, signed informed consent forms, consultant letters, and patient screening and enrollment logs.

These documents must be kept on file by the investigator for a period of 2 years following the date the marketing application is approved for the drug indication for which it is being investigated. If no application is to be filed or if the application is not approved for such

indication, all records pertaining to the conduct of the clinical study must be adequately maintained until 2 years after the investigation is discontinued and the regulatory authorities are notified or longer as required by applicable regulatory authorities.

The investigator must not destroy any records associated with the study without receiving approval from the sponsor. The investigator must notify the sponsor in the event of accidental loss or destruction of any study records and should notify the sponsor of any reassignment of study records to another party or move to another location.

15.4. Study Monitoring

Qualified representatives of the sponsor or sponsor designees (study monitors) will monitor the study according to a predetermined monitoring plan. The investigator must permit the study monitors to periodically review all eCRFs and source documents supporting the participation of each patient in the study. The eCRFs and other documentation supporting the study must be kept up to date by the investigator and the staff at the study site. These study materials must be available for review by the study monitor, and/or other qualified representatives of the sponsor, at each monitoring visit and must be provided in a way such that the patient's confidentiality is maintained in accordance with local institution, state, country, and federal requirements.

15.5. Audits and Inspections

At some point during the study or after the study, appropriately qualified personnel from the sponsor's Quality Assurance group, or their authorized representative, or a representative from a regulatory authority may visit the investigator to conduct an inspection of the study and the site. During this audit, the investigator agrees to give the auditor direct access to all relevant documents supporting the eCRFs and other study-related documents and to discuss any findings with the auditor. In the event of an inspection by a regulatory agency, the investigator agrees to give the inspector direct access to all relevant documents and to discuss any findings with the inspector.

16. PUBLICATION POLICY

By signing the study protocol, the investigator and his or her institution agree that the results of the study may be used by G1 Therapeutics for the purposes of national and international registration, publication, and information for medical and pharmaceutical professionals. If necessary, the authorities will be notified of the investigator's name, address, qualifications, and extent of involvement.

Initial publication of the results of this study will be of a cooperative nature that may include authors representing the sponsor, investigator(s), and collaborating scientists. Independent publications by involved individuals may follow. Investigators and their institutions agree not to publish or publicly present any interim results of studies without the prior written consent of G1 Therapeutics.

At least 60 days prior to expected submission to the intended publisher or meeting committee, the investigator will submit a copy of the desired presentation (oral or written) or publication manuscript to the sponsor. This review period may be shortened upon mutual consent where circumstances require expeditious review. The sponsor reserves the right to request modification of any publication, presentation or use by the investigator if such activity may jeopardize a patent application, an existing patent, or other proprietary rights. The sponsor shall determine order of authorship of any publication combining all clinical results of this study.

18. APPENDICES

APPENDIX 1: Common Terminology Criteria for Adverse Events (CTCAE) –Version 4.03

The NCI CTCAE Version 4.03 (CTCAE 4.03 14 June 2010) can be accessed from the following National Cancer Institute (NCI) website:

http://evs.nci.nih.gov/ftp1/CTCAE/About.html

http://evs.nci.nih.gov/ftp1/CTCAE/CTCAE_4.03_2010-06-14_QuickReference_5x7.pdf

APPENDIX 2: Prescribing Information for Osimertinib

Tagrisso® (osimertinib) PI, March 2017 link: https://www.azpicentral.com/tagrisso/tagrisso.pdf#page=1

APPENDIX 3: Drugs that May Prolong the QT Interval

The drugs listed in this section are taken from information provided by The Arizona Center for Education and Research on Therapeutics and The Critical Path Institute, Tucson, Arizona and Rockville, Maryland. Ref: http://www.arizonacert.org/medical-pros/drug-lists/drug-lists.htm.

Drugs Known to Prolong the QT Interval

The following drugs are known to prolong QT interval or induce Torsades de Pointes and should not be combined with osimertinib. Recommended withdrawal periods following cessation of treatment with these agents are provided in Table 18-1.

Table 18-1 Drugs Known to Prolong the QT Interval

Contraindicated Drug	Withdrawal Period Prior to Initiating Osimertinib
Clarithromycin, droperidol, erythromycin, procainamide	2 days
Cisapride, disopyramide, dofetilide, domperidone, ibutilide, quinidine, sotalol, sparfloxacin, thioridazine	7 days
Bepridil, chlorpromazine, halofantrine, haloperidol, mesoridazine	14 days
Levomethadyl, methadone, pimozide	4 weeks
Arsenic trioxide	6 weeks ^a
Pentamidine	8 weeks
Amiodarone, chloroquine	1 year

a Estimated value as pharmacokinetics of arsenic trioxide has not been studied.

Drugs that May Possible Prolong the QT Interval

Use of the drugs in Table 18-2 is permitted (notwithstanding other exclusions and restrictions) provided the patient has been stable on therapy for the periods indicated.

Table 18-2 Drugs that May Prolong QT Interval

Drug	Minimum Treatment Period on Drug Prior to Initiating Osimertinib
Alfuzosin, chloral hydrate, ciprofloxacin, dolasetron, foscarnet, galantamine, gemifloxacin, isridipine, ketoconazole, levofloxacin, mexiletine, nicardipine, octreotide, ofloxacin, ondansetron, quetiapine, ranolazine, telithromycin, tizanidine, vardenafil, venlafaxine, ziprasidone	2 days
Amantadine, amitriptyline, amoxapine, clozapine, doxepin, felbamate, flecainide, ibutilide, quinidine, sotalol, sparfloxacin, thioridazine, fluconazole, fosphenytoin, gatifloxacin, granisetron, imipramine, indapamide, lithium, moexipril/HCTZ, moxifloxacin, risperidone, roxithromycin, sertraline, trimethoprin-sulfa, trimipramine, voriconazole	7 days
Azithromycin, citalopram, clomipramine, itraconazole, nortriptyline, paroxetine, solifenacin, tacrolimus	14 days
Fluoxetine	5 weeks
Protriptyline	6 weeks
Tamoxifen	8 weeks

APPENDIX 4: Drugs Known to Interact with the P-glycoprotein, BCRP, MATE1, MATE2-K, and OCT1 and 2 Membrane Transporters

The following lists of drugs known to interact with membrane transporters is a representative sample of potentially G1T38-interacting drugs. Caution should be exercised if any of these drugs are concurrently used with G1T38. Use of strong inhibitors of BCRP is prohibited.

Strong Inhibitors of P-gp (use with caution):

- Cyclosporine
- Elacridar
- Ketoconazole
- Reserpine
- Ritonavir
- Tacrolimus
- Valspodar
- Verapamil
- Zouquidar
- Amiodarone
- Carvedilol
- Clarithromycin
- Dronedarone
- Itraconazole
- Lapatinib
- Propafenone

- Quinidine
- Ranolazine
- Telaprevir

Strong Inhibitors of BCRP (use prohibited):

- Elacridar
- Fumitremorgin C
- Ko134
- Ko143
- Novobiocin
- Sulfasalazine
- Curcumin
- Cyclosporine A
- Eltrombopag

Strong Inducers of P-gp (use with caution):

- Carbamazepine
- Phenytoin
- Rifampin
- St. John's Wort
- Tipranavir

MATE1 and MATE2-K Substrates (use with caution):

- Metformin
- MPP+
- Tetraethylammonium (TEA)
- Dofetilide

OCT1 and OCT2 Substrates (use with caution):

- OCT1: metformin, oxaliplatin, aciclovir, ganciclovir
- OCT2: metformin, pindolol, procainamide, ranitidine, amantadine, amiloride, oxaliplatin, varenicline, cisplastin, debrisoquine, proplanolol, guanidine, D-tubocurarine, pancuronium

P-gp Substrates (use with caution):

- Digoxin
- Fexofenadine
- Loperamide
- Quinidine
- Talinolol
- Vinblastine
- Dabigatran

BCRP Substrates (use with caution):

- 2-amino-1-methyl-6-phenylimidazo[4,5-b]pyridine (PhIP)
- Coumestrol
- Daidzein
- Dantrolene
- Estrone-3-sulfate
- Genistein
- Prazosin
- Sulfasalazine
- Rosuvastatin

APPENDIX 5: RECIST Version 1.1 Time Point Response Evaluation Guidelines for Patients with Nontarget Disease Only

Nontarget Lesions	New Lesions	Overall Response
CR	No	CR
Non-CR/non-PD	No	Non-CR/non-PD ^a
Not all evaluated	No	NE
Unequivocal PD	Yes or No	PD
Any	Yes	PD

CR = complete response; NE = not evaluable; PD = progressive disease

Source: Table modified from Eisenhauer EA, Therasse P, Bogaerts J, et al. New response evaluation criteria in solid tumors: revised RECIST guideline (version 1.1). Eur J Cancer. 2009;45:228-247.

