- 8. *Part 1:* Patients receiving medications that raise gastric pH within 7 days prior to first dose of study drug such as proton pump inhibitors (eg, omeprazole, pantoprazole, lansoprazole, esomeprazole, rabeprazole, dexlansoprazole), H2 blockers (eg, nizatidine,

- famotidine, cimetidine, ranitidine), and antacids (eg, sodium bicarbonate, calcium carbonate, aluminum-based antacids, magnesium compounds, alginic acid).
- 9. Any unresolved toxicities from prior surgeries or therapy of > Grade 1 (CTCAE, Version 4.03) at the time of starting study drug with the exception of alopecia (any grade) and platinum therapy-related peripheral neuropathy (> Grade 2)
- 10. Known active uncontrolled or symptomatic central nervous system (CNS) metastases, carcinomatous meningitis, or leptomeningeal disease as indicated by clinical symptoms, cerebral edema, and/or progressive growth. Patients with a history of CNS metastases or cord compression are eligible if they are currently asymptomatic and clinically stable off anticonvulsants and steroids for at least 28 days prior to first dose of G1T38.
- 11. Any evidence of severe or uncontrolled systemic diseases, including uncontrolled hypertension and active bleeding diatheses, which in the investigator's opinion makes it undesirable for the patient to participate in the study or which would jeopardize compliance with the protocol
- 12. Known chronic, active infection including but not limited to hepatitis B virus, hepatitis C virus, tuberculosis, and human immunodeficiency virus (HIV); screening for chronic conditions is not required
- 13. Any of the following cardiac criteria:
 - a. Mean resting corrected QT interval (QTc) > 470 msec obtained from 3 electrocardiograms (ECGs), using the screening clinic ECG machine derived QTc value
 - b. Any clinically important abnormalities in rhythm, conduction, or morphology or resting ECG, eg, complete left bundle branch block, third degree heart block, second degree heart block, PR interval > 250 msec
 - c. Any factors that increase the risk of QTc prolongation (see Appendix 3 for list of drugs) or risk of arrhythmic events such as heart failure, hypokalemia, congenital long QT syndrome, family history of long QT syndrome or unexplained sudden death under 40 years of age in first degree relatives, or any concomitant medication known to prolong the QT interval

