8.1. Treatments Administered

Study drugs will be administered as follows for each cohort in Part 1 of the study:

- Cycle 1 Day -16: single oral dose of G1T38
- Cycle 1 Day -15: no study drug administered
- Cycle 1 Days -14 to -3: oral once-daily doses of osimertinib
- Cycle 1 Day -2: single oral dose of osimertinib and G1T38
- Cycle 1 Day -1: single oral dose of osimertinib

Beginning with Cycle 1 Day 1, oral once-daily doses of G1T38 and osimertinib will commence (Figure 8-1).

Figure 8-1 Study Schema: Part 1

PTV = Post-Treatment visit

There is no Day 0 in the study. A treatment cycle is defined as 28 days.

In Part 2, eligible patients will be randomized (1:1) to receive osimertinib or G1T38 (at the RP2D) + osimertinib. Randomized patients will begin once-daily oral dosing of osimertinib or G1T38 + osimertinib on Cycle 1 Day 1 (Figure 8-2).

Screening Treatment PTV Survival Cycle 1 Day 1 until PD All patients to have All natients to be **Optional Crossover** followed every RECIST 1.1 Osimertinib assessment every Patients begin 8 weeks for PFS and 8 weeks until disease OS until disease post-progression progression G1T38 + osimertinib progression with RECIST assessments every Randomize 8 weeks All patients to have All patients to be RECIST 1.1 followed every G1T38 + 8 weeks for PFS and assessment every Osimertinib 8 weeks until disease OS until disease progression progression

Figure 8-2 Study Schema: Part 2

PTV = Post-Treatment visit

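### Protocol Appendix 3 lists five QT-prolonging drugs as contraindicated with osimertinib in Table 18-1 and as permitted in Table 18-2

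*Protocol*

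**What the plan says.** Appendix 3 of the protocol holds two drug lists with opposite purposes.

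Table 18-1 covers drugs known to prolong the QT interval. Its lead-in reads "The following drugs are known to prolong QT interval or induce Torsades de Pointes and should not be combined with osimertinib". The column heading calls the drugs contraindicated, and the second column gives a recommended withdrawal period before osimertinib. The 7-day row ends "dofetilide, domperidone, ibutilide, quinidine, sotalol, sparfloxacin, thioridazine".

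Table 18-2 covers drugs that may prolong the QT interval. Its lead-in reads "Use of the drugs in Table 18-2 is permitted (notwithstanding other exclusions and restrictions) provided the patient has been stable on therapy" for the listed period. The second column is the minimum time on the drug before osimertinib starts. The 7-day row contains the run "flecainide, ibutilide, quinidine, sotalol, sparfloxacin, thioridazine, fluconazole".

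Exclusion 13c in Section 7.1.2 refers to this appendix. It opens "Any factors that increase the risk of QTc prolongation (see Appendix 3 for list of drugs" and closes "or any concomitant medication known to prolong the QT interval".

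For Part 1, Section 8.1 gives the first study dose as "Cycle 1 Day -16: single oral dose of G1T38" and the osimertinib run-in as "Cycle 1 Days -14 to -3: oral once-daily doses of osimertinib".

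**The concern.** A drug cannot be both contraindicated with osimertinib and permitted with it. A site that checks a patient's medication against Table 18-2 alone would read five contraindicated drugs as allowed after a week of stable use. A site that checks Table 18-1 would stop them.

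Appendix 3 is an operating list. Exclusion 13c sends sites to it, and the concomitant-medication rules in Sections 8.5.1 to 8.5.6 and 8.8 contain no QT-drug rule of their own. Section 4.5 names QTc prolongation among the less frequent but potentially more severe osimertinib-related events. What is at stake is a clear safety instruction at entry, and for the continued use of a drug already being taken. No statistical quantity is involved.

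**Working it through.** The plan states no figure on this point to reproduce. The check compares the two lists drug by drug.

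**Counts by row**

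- Table 18-1: 4 (2 days) + 9 (7 days) + 5 (14 days) + 3 (4 weeks) + 1 (6 weeks) + 1 (8 weeks) + 2 (1 year) = 25 drugs.
- Table 18-2: 22 (2 days) + 27 (7 days) + 8 (14 days) + 1 (5 weeks) + 1 (6 weeks) + 1 (8 weeks) = 60 drugs.

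**Overlap.** Exactly five drugs are in both tables: 5/25 = 20% of Table 18-1 and 5/60 = 8.3% of Table 18-2.

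| Drug | Table 18-1 | Table 18-2 |
|---|---|---|
| Ibutilide | do not combine; off 7 days before | permitted; on at least 7 days before |
| Quinidine | same | same |
| Sotalol | same | same |
| Sparfloxacin | same | same |
| Thioridazine | same | same |

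**Which table is wrong.** The 7-day row of Table 18-2 has 27 names. The five occupy positions 8 to 12, between flecainide and fluconazole, where they break the alphabetical order. They match the last five names of the Table 18-1 7-day row, in the same sequence. Without them, the remaining 27 − 5 = 22 names are in strict alphabetical order. The Table 18-1 row is alphabetical with the five in place. This points to text copied from Table 18-1 into Table 18-2.

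**Timing in Part 1.** Osimertinib starts on nominal Day −14, and 7 days earlier is Day −21. The first study dose is on Day −16, and −16 − (−21) = 5. A patient who meets the Table 18-2 minimum has therefore been on the drug since at least 5 days before the first study dose. If the +1 day window that Table 9-1 allows for Day −14 is used, the figures are Day −20 and 4 days. In both cases the drug is already a concomitant medication at entry, so the closing clause of 13c would bar the patient if the site applies it.

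**Other rules that reach the five.** Oral quinidine is barred by exclusion 5b and Section 8.5.1 as a CYP3A4 substrate. Neither rule names the other four, whose status rests on Appendix 3 and 13c.

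**The case against.** The strongest reply is that binding text already settles entry. The closing clause of 13c uses the same description as the title of Table 18-1, so it favours that table. Patients with a mean QTc above 470 msec are excluded, triplicate ECGs are scheduled, and treatment is interrupted for QTcF above 500 msec. Part 2 will not be conducted (SAP Section 1), and the documents do not show that any patient took one of these drugs.

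Most of this stands, and it is why the point is minor. It does not remove the conflict. The lead-in to Table 18-2 grants its permission *notwithstanding* other exclusions; read literally, that overrides 13c. The safeguards act on a measured QTc and do not correct the list. After Day −2, the next ECG that Section 10.6.5 schedules in Part 1 is on Cycle 2 Day 1.

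A second reply is that the duplicated block could come from the way the PDF was read. This cannot be fully excluded. It is unlikely, because the row is otherwise intact and the protocol's list of tables puts the two tables on different pages (100 and 101).

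A reader might also infer two stronger claims that the documents do not support:

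- **That the tables require a patient to be both off and on the drug for the same 7 days.** Table 18-1 only recommends its withdrawal periods, and Table 18-2 gives a conditional permission and obliges nobody to take a drug. The conflict is between contraindicated and permitted.
- **That *notwithstanding* should become *subject to*.** The word is ambiguous for the CYP3A4 inhibitors and substrates in Table 18-2, but this edit would do harm. It would place the whole table under 13c, whose opening words cite all of Appendix 3, and so would cancel the permission for every remaining drug.

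**Conclusion.** The inconsistency is real and minor. Five named drugs have opposite statuses in two tables of the same appendix, and the order of the names indicates that Table 18-2 is the one in error. This rests on the tables as extracted; a look at the source page would close the small remaining doubt about a reading artefact.

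The practical risk is small, for the reasons conceded above. The number of patients affected cannot be estimated, because the documents give no rate of use of these drugs. The Part 1 ceiling of 36 is an enrolment limit and not a count of patients exposed to the conflict. A reader might infer that G1T38 pharmacokinetics, DLT assessment or efficacy results are compromised; nothing in the documents supports that.

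**What to change.** Delete ibutilide, quinidine, sotalol, sparfloxacin and thioridazine from the 7-day row of Table 18-2, so that Table 18-1 governs. The row then has 22 drugs and the table 60 − 5 = 55. Leave the lead-in to Table 18-2 and exclusion 13c as they are.

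The cost is a protocol clarification letter or a minor amendment that removes five names from one table row. The SAP, the sample size and the analyses do not change.
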